## **6.7.8. Derived Efficacy Endpoints**

### **6.7.8.1. Subject-Reported Attack**

A subject-reported attack is any attack reported on the HAE Attack Details eCRF page. Each reported attack will count as a separate attack, even if the time periods for the attacks are overlapping.

### **6.7.8.2. Adjusted Attack**

Subject-reported attacks reported must meet the following criteria (applied in order) for inclusion in effectiveness analyses:

- Attack must include at least 1 symptom of swelling
- Subject response to diary question, “In retrospect, could there be an alternative explanation for your symptoms other than an HAE attack (ie, allergic reaction, viral cold etc.)?” must be “no”.
- Attack must be unique (attack began > 24 hours from the end of the prior attack).
- Any attack that begins within 24 hours from the end of a prior attack will be combined with the prior attack.
- If the entire adjusted attack is untreated, it must have a duration > 24 hours

Using the above criteria, adjusted attacks will be determined programmatically. For adjusted attacks that span 2 or more subject-reported attacks, attack triggers, locations, symptoms, duration, and other characteristics will be based on the information from each component subject-reported attack. Additionally, the start date/time of the adjusted attack will be the start date/time from the first attack and then end date/time of the adjusted attack will be the end date/time from the last attack being collapsed programmatically.

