#### **6.7.8.7. Attack Duration**

The duration of each subject-reported attack will be calculated in hours, based on the start and stop date and time of the subject-reported attack (time the attack finished). For an adjusted attack that includes more than one subject-reported attack, the duration is calculated from the start of the first subject-reported attack to the end of the last subject-reported attack that has been combined into one adjusted attack. Similarly, the duration of the attack from start of the attack to time that the worst was over will also be calculated.

All subject-reported attack durations will be included in listings and those included in adjusted attacks will be denoted. Adjusted attack duration will be summarized.

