### **6.8.5. Incomplete Date and Time for a Subject-Reported Attack**

For HAE attacks reported with a missing stop date and or time, the following algorithm will be applied:

- Missing start time but start date present:

The start time will be set to 12:00PM.

- Missing start date and time:

The start date will be set to the diary date for which the question was answered “Yes”.  
The start time will be set to 12:00PM

- Missing stop time, but stop date present:

The stop time will be set to 11:59PM

- Missing stop date and time:

The stop date will be set to the attack start date, the stop time will be set to 11:59PM

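### A missing attack start time set to noon can fall after the recorded stop, and the end of a combined attack is not defined for nested reports

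*SAP*

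**What the plan says.** **Missing start time.** Where the start date is known but the time is not, SAP 6.8.5 directs: "The start time will be set to 12:00PM". There is no exception for a stop recorded before noon on the same date, and no other section deals with a stop that precedes its start.

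**Overlap.** SAP 6.7.8.1: "Each reported attack will count as a separate attack, even if the time periods for the attacks are overlapping".

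**Combining.** SAP 6.7.8.2 requires uniqueness, "Attack must be unique (attack began > 24 hours from the end of the prior attack", and its next bullet adds: "Any attack that begins within 24 hours from the end of a prior attack will be combined with the prior attack". An adjusted attack that is wholly untreated must last more than 24 hours to be included.

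**End of a combined attack.** SAP 6.7.8.2 takes the start from the first attack, and says the "end date/time of the adjusted attack will be the end date/time from the last attack being collapsed programmatically". SAP 6.7.8.7 measures duration "from the start of the first subject-reported attack to the end of the last subject-reported attack". Neither section says whether *last* means the component that starts last or the one that ends last. SAP 6.7.8.2 does say that the characteristics of a combined attack, duration among them, draw on every component.

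**Use.** SAP 6.7.8.7 calculates a duration for every subject-reported attack. The table list in SAP 13.1 summarises durations of adjusted attacks (14.2.1.12) and of subject-reported attacks (14.2.1.13).

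**The concern.** Protocol 7.1.2 leaves the confirmation or rejection of attacks to pre-defined rules in the SAP, and SAP 6.7.8.2 applies them by program. The rules therefore have to give one sensible answer for every record that the plan accepts.

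The noon rule does not. It can place the start of an attack after its own recorded end.

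The combining rule is sound for attacks that follow one another, and for partial overlaps in which the later report also ends later. It is not clearly sound for a short report nested inside a longer one. There, the last report in sequence ends before the first one does.

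At stake are attack duration, inclusion under the 24-hour rule for untreated attacks and, through inclusion, the adjusted attack rate.

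**Working it through.** The plan gives no worked example of either rule, so there is no figure to reproduce. The sequences below are constructed; only the rules come from the SAP. Duration = end minus start. Gap = start minus the end of an earlier attack. An adjusted attack is kept if it was treated or lasted more than 24 h, assuming the swelling and alternative-explanation criteria are met.

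**1. Noon start, stop earlier the same day (SAP 6.8.5)**
- Start date known, start time missing, stop 09:00 that day.
- As written: 09:00 - 12:00 = **-3 h**.
- The true start lies between 00:00 and 09:00, so the true duration is 0 to 9 h and the error is 3 to 12 h.
- If treated, the attack passes the 24-hour rule, which applies only to untreated attacks, and is counted with a negative duration. If untreated and stand-alone, it drops out of the adjusted set, as it should at 9 h or less. The negative value still goes into the subject-reported duration table.
- The imputed time can also split an attack. Let a treated attack end at 10:00 on Day 1, and let the record above be a treated attack on Day 2. Its real start is no later than 09:00, so the real gap is at most 23 h and the two should merge. The imputed gap, Day 1 10:00 to Day 2 12:00, is 26 h, so they count as two.

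**2. Nested report (SAP 6.7.8.2 and 6.7.8.7)**

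| Case | A | B | End of last in sequence | Latest end |
|---|---|---|---|---|
| Duration | Day 1 08:00 to Day 4 08:00 | Day 2 08:00 to 20:00 | Day 2 20:00: 36 h | Day 4 08:00: 72 h |
| Both untreated | Day 1 08:00 to Day 2 20:00 | Day 1 12:00 to 20:00 | Day 1 20:00: 12 h, excluded | Day 2 20:00: 36 h, included |

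**3. Third report in the first case, starting Day 4 07:00**
- Gap from the end of B (Day 2 20:00): 4 + 24 + 7 = 35 h. This exceeds 24 h, so it is a new attack.
- Relative to the end of A (Day 4 08:00), it starts 1 h earlier, while A is still running.
- The result turns on which end is used. The uniqueness bullet refers to *the* prior attack and the merge bullet to *a* prior attack. Under the second wording the report joins A.

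**4. Scale for one subject**
- The rate is attacks × 28 / days (SAP 6.7.8.3). One attack gained or lost moves a monthly rate by 1 × 28/28 = 1.0. Over 96 weeks (672 days) it moves the rate by 1 × 28/672 = 0.04.
- For comparison, Protocol 5.2.2 gives interim means of 1.18, 1.01 and 0.81 attacks per month at Months 1, 6 and 12 in the 150 mg group.

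**The case against.** **The word *last* may be innocent.** It can mean the component that ends last, and the statement that duration draws on every component supports that reading. Both table cases then give the longer figure. This stands. Paired with *first*, last in sequence is the more natural reading, but the text does not settle it.

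**Overlap is not nesting.** A partial overlap is handled correctly on either reading; only a report wholly inside another causes trouble. This stands, and the frequency of such reports is unknown.

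**A reader might infer that a third report is necessarily double-counted.** The documents do not support that. It happens only if the gap is measured from the immediately preceding report or from a collapsed end that has been cut short. The merge bullet avoids it.

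**A reader might infer that symptom days fall from 4 to 2 in the first nested case.** SAP 6.7.8.4 counts days with a symptom reported during an adjusted attack. It does not clearly direct that A's own reported days after B ended be discarded.

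**The lead-in to SAP 6.8.5 mentions only a missing stop.** Read literally, a known 09:00 stop would fall outside the algorithm. However, the section title covers incomplete dates and times generally, and its first two bullets deal with missing starts. The literal reading is weak, though the lead-in should be corrected.

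**There are safeguards.** Edit checks (SAP 6.3) and diary correction by the subject (Protocol 11.2.2) should make such records rarer. All durations are listed, and the subject-reported rate is also computed. These measures limit the harm but do not change the rule.

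**Conclusion.** The noon rule is a fault in the text as it stands. It needs no interpretation, gives -3 h for a 09:00 stop, and nothing elsewhere in the plan prevents the value from reaching the duration tables.

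The end of a combined attack is an ambiguity with a real consequence. If *last* is read as last in sequence, a nested report shortens the combined attack (36 h against 72 h) and can wrongly exclude an untreated one (12 h against 36 h). If it is read as latest-ending, there is no error. Two competent programmers could obtain different counts from the same data.

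It would go too far to conclude that the attack rates are materially biased. The sequences are constructed, and the documents give no frequency of nested reports or missing start times. SAP 8.1 treats effectiveness as secondary and without formal testing. The effect on mean rates cannot be sized, and the primary safety objective is not touched. The point merits a correction before database lock, and no more than that.

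**What to change.** Make three edits to the SAP before lock:

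1. In 6.7.8.2 and 6.7.8.7, define the end of an adjusted attack as the latest end date/time among all its components.
2. In 6.7.8.2, measure the 24-hour gap from the latest end reached so far, and use the same wording in the uniqueness and merge bullets.
3. In 6.8.5, require that an imputed start cannot fall after the recorded stop, and widen the lead-in to cover missing starts. One workable convention is 12:00, or the midpoint between 00:00 and the stop time if the stop is before noon that day. A 09:00 stop then gives a 04:30 start and 4.5 h. Other conventions would serve, provided one is fixed in advance.

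The cost is a small code change and no new data. Interim adjusted-attack results already exist for the 20 August 2019 cut-off (Protocol 5.2.2). If the program behind them used a different rule, the interim and final figures would need a short reconciliation.

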### **6.7.8.3. Attack Rate**

The observed attack rate will be computed as the number of attacks per month, where 1 month is defined as a 4-week period (28 days).

In general, the formula for computing an attack rate is the number of attacks meeting the attack criteria divided by the duration of the reporting period of interest.

$$\text{Attack Rate} \left( \frac{\text{attacks}}{\text{month}} \right) = \frac{\text{Number of Attacks} * 28}{\text{Duration of Treatment Period of Interest}}$$

For subjects who complete the reporting period of interest, duration of reporting period of interest is defined as the last day in the reporting period – first day in reporting period + 1. For subjects who discontinue treatment prematurely in the reporting period of interest, the duration of reporting period of interest is defined as (last day of treatment +1) – first day in reporting period + 1. For example, if a subject receives the last treatment on Day 13 of Month 3 with 2 attacks between Day 1 and Day 14, that subject will be considered to have had a rate of 4 attacks/month ( $2 \times 28/14 = 4$ ) for Month 3. Both the reporting period and the treatment period have been adjusted to include an additional day as the subject prematurely discontinued dosing in Month 3.

### **Subject-Reported Attack Rate**

Subject-reported attack rates will be computed for the entire dosing period.

### **Adjusted Attack Rate by Location**

Adjusted Abdominal-only, Peripheral, and Mixed attack rates will be computed using the location definitions provided in Section 6.7.8.12.

#### **6.7.8.4. Number and Proportion of Days with Angioedema Symptoms**

The number of days with angioedema symptoms is the sum of the days during the reporting period for which at least one symptom is reported during an adjusted HAE attack. The definition of the reporting period will be defined for subjects who discontinue in the same manner as for the attack rate calculation (see Section 6.7.8.3).

The percentage of days with angioedema symptoms is derived as the number of days with angioedema symptoms divided by the duration of the reporting period of interest. The calculation will be performed similarly to the calculation of the attack rate (see Section 6.7.8.3).

#### **6.7.8.5. Durability of Response**

The durability of response is defined as the adjusted attack rate trend over time. Adjusted attack rates by month (28-day blocks of time, starting with Day 1) will be calculated and summarized.

#### **6.7.8.6. Subjects Who Are Attack Free**

A subject who completes dosing in the reporting period of interest and has no adjusted attacks during this same period is considered attack free. Subjects with no adjusted attacks in the reporting period but who discontinue before the end of the period or who experience adjusted attacks in the period are not considered attack-free. For the purposes of this analysis, the reporting period is zero to 24 weeks zero to 48 weeks, and for the entire study.

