The proportion of days with angioedema symptoms was generally similar for both dose groups and declined over time: during Month 1 the median proportion of days with symptoms was 7.1%; during Month 6 the median proportion of days with symptoms was 3.6%; and during Month 12 the median proportion of days with symptoms was 0.0%.

During the first 24 weeks of study, 22 subjects (9.8%) treated with BCX7353 remained attack free, with slightly more subjects in the BCX7353 150 mg group (11.2%) remaining attack free compared with the BCX7353 110 mg dose group (8.0%). During the first 48 weeks of study, 8 subjects (5.0%) treated with BCX7353 remained attack free, with slightly more subjects in the BCX7353 150 mg group (5.8%) remaining attack free compared with the BCX7353 110 mg dose group (3.6%).

A total of 28 of 227 subjects (12.3%) discontinued treatment in the first 48 weeks of the study due to perceived lack of efficacy, with fewer subjects discontinuing treatment in the BCX7353 150 mg dose group compared to the 110 mg dose group (11 [8.7%] vs. 17 [17.0%], respectively). Twenty of the 28 subjects who discontinued study drug due to a perceived lack of efficacy discontinued prior to Week 12. The proportions of subjects who discontinued BCX7353 due to a perceived lack of efficacy was higher for those subjects who had reported either that they had discontinued androgen use < 2 weeks prior to their first dose of BCX7353 (20.0%) or had used androgens for ≥ 10 years (18.2%), compared to subjects who had never used androgens (12.2%). Twelve of the 28 (42.9%) subjects who discontinued BCX7353 due to a perceived lack of efficacy had used androgen therapy for ≥ 10 years before their first dose of BCX7353. Eight of the 28 (28.6%) subjects who discontinued BCX7353 due to a perceived lack of efficacy and had discontinued androgen therapy < 2 weeks before their first dose of BCX7353.

The median duration of an attack was shorter for subjects treated with BCX7353 150 mg vs. 110 mg (median of 17.7 vs. 28.0 hours). This difference was independent of attack location (ie, abdominal-only, peripheral-only, and mixed).

Overall, subjects assessed about 34% of their attacks as negligible or mild in severity with approximately 60% of attacks resulting in no restriction or a slight restriction of daily activities. Overall, approximately 61% of attacks had no or a slight effect on the subject's appearance. There were no notable differences between the dose groups.

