7. OVERALL STUDY DESIGN AND PLAN

This is a single-arm open-label study designed to evaluate the long-term safety of prophylactic treatment with daily oral BCX7353 in subjects with HAE. The study will also evaluate the long-term effectiveness and impact on QoL or general well-being of subjects who receive BCX7353 prophylactic treatment, and the subject's satisfaction with the medication. Based on the final results from Part 1 of the randomized, double-blind, placebo-controlled efficacy study (BCX7353-302), the dose of BCX7353 used in this study is 150 mg QD.

Subjects may be enrolled once all eligibility criteria and study requirements are met. On-treatment study visits will occur at Weeks 4, 12, 24, 48, 72, and 96. An independent DMC has been reviewing the safety data from this study in concert with the accumulating safety information generated across the BCX7353 clinical development program. The DMC met at a frequency of approximately every 12 weeks until a total of approximately 200 subjects across the Phase 3 Study, BCX7353-302, and the current study (BCX7353-204) completed 48 weeks of dosing with active drug. Since a total of over 200 subjects have completed 48 weeks across the studies, the DMC is now provided with data every 6 months until the last subject completes the study or approval is obtained in the first country globally. A formal meeting of the DMC members will not be required; however, if the data review identifies any concern, the DMC members may elect to hold a formal DMC meeting. In addition, the emergence of a new, clinically significant safety signal may prompt an ad hoc DMC review.

Approximately 475 subjects will be enrolled into the study, with approximately 250 subjects planned to be enrolled in the US. Subjects will be eligible to receive BCX7353 for up to 96 weeks, until the product becomes commercially available, or until the Sponsor discontinues development of the product for the prevention of angioedema attacks, whichever comes first.

A study schema is shown in [Figure 1](#).

[figure not shown]
All subjects will be instructed to complete their diaries to document all angioedema attacks that occur.

Acute attacks of angioedema will be treated in accordance with the subject's normal standard of care. Treatment for acute attacks of HAE will not be provided by the Sponsor.

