## **6.4. Data Presentation Conventions**

Continuous variables (eg, age) are summarized using descriptive statistics (the number of subjects with available data, the mean, standard deviation (SD), median and minimum and maximum). Categorical variables (eg, race) are summarized using counts and percentages. Percentages are calculated using the total subjects per treatment group.

The following conventions are applied to all data presentations and summaries.

- For continuous variables, all mean and median values are formatted to 1 more decimal place than the measured value. SD values are formatted to 2 more decimal places than the measured value. Minimum and maximum values are presented with the same number of decimal places as the measured value.
- For categorical variables, the number and percentage of responses are presented in the form XX (XX.X%) where the percentage is in the parentheses.

- Date variables are formatted as DDMMYYYY for presentation. Time is formatted in military time as HH:MM for presentation.
- Wherever possible, data will be decimal aligned.

The table of contents as part of this SAP along with the table and listing shells provided in separate documents provide the expected layout and titles of the tables, listings and figures. Any changes to format, layout, titles, numbering, or any other minor deviation will not necessitate a revision to the SAP, nor will they be considered as deviations from planned analyses. Only true differences in the analysis methods or data handling will necessitate such documentation. The appropriate listings supporting the tables will be included and are not necessarily specified in the individual sections throughout the document.

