## **6.8. Handling of Missing Data**

### **6.8.1. Missing Effectiveness Endpoints**

For subjects who prematurely discontinue the study, all available data will be included for the key safety and effectiveness analyses. No imputation for missing data will occur.

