### **8.3. Analysis of the Effectiveness Endpoints**

#### **8.3.1. Effectiveness Analysis**

The effectiveness analysis is comprised of multiple endpoints (Section 3.2.2) and will be conducted on the safety population.

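### Attack-free subjects whose treatment ends at commercial availability before Week 24 or 48 would count as failures, because the SAP's attack-free rule does not foresee that stop

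*SAP*

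**What the plan says.** SAP 6.7.8.6 gives both halves of the rule. "A subject who completes dosing in the reporting period of interest and has no adjusted attacks during this same period is considered attack free"; and subjects "who discontinue before the end of the period or who experience adjusted attacks in the period are not considered attack-free". The reason for stopping plays no part. On the periods it says "the reporting period is zero to 24 weeks zero to 48 weeks, and for the entire study".

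The section names no denominator. The general convention in SAP 6.4 supplies one: "Percentages are calculated using the total subjects per treatment group". SAP 8.3.1 adds that the effectiveness analysis "will be conducted on the safety population", and SAP 6.8.1 that "No imputation for missing data will occur".

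The current protocol (section 7; likewise the synopsis and section 10.1) sets a ceiling of 96 weeks and otherwise continues treatment only "until the product becomes commercially available, or until the Sponsor discontinues development of the product for the prevention of angioedema attacks, whichever comes first". Section 14.4 lists commercial availability among the grounds for terminating the study. Sections 8.3.1, 10.1 and 10.3.5 describe subjects who move to another source of the drug as discontinuing the study.

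The SAP's revision table stops at protocol version 5.0. Its treatment-duration text names only 96 weeks or the end of development. Commercial availability does not appear.

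SAP 8.3.1.5 treats the same subjects differently: in the Kaplan-Meier analysis of time to first adjusted attack, a subject without one is censored when study treatment stops.

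**The concern.** A subject who has had no attack and is taken off study supply because the drug can now be prescribed has not failed treatment. The SAP text nevertheless leaves that subject in the denominator and out of the numerator. The 24- and 48-week attack-free percentages would then depend partly on when the product reached the market relative to enrolment. Early and late enrollees would not be comparable, and neither would the interim and final figures.

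The possibility is not remote. Protocol 5.4.1 says that the US and Japanese filings were complete when this version was written. At the interim cut-off of 20 August 2019, 227 subjects had been treated out of about 475 planned, so about 248 had yet to start.

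**Working it through.** **Inputs.** Interim results from Protocol 5.2.2: 227 treated; 103 completed Week 48; 57 discontinued before 48 weeks; attack-free over 48 weeks 8 subjects, 5.0% (150 mg 5.8%, 110 mg 3.6%); attack-free over 24 weeks 22 subjects, 9.8% (11.2% and 8.0%). Planned enrolment from Protocol 8.1: about 475, of whom about 250 in the US. The share stopped by commercial availability is not in the documents; a range of 5% to 50% is assumed.

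**1. Reproduce the interim figures.** The protocol prints counts and percentages but no denominators, so these are inferred.

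- 48 weeks: 8/160 = 5.0%, with 6/104 = 5.8% and 2/56 = 3.6%. Also 103 + 57 = 160. A total of 159 fits the rounding as well.
- 24 weeks: 22/225 = 9.8%, with 14/125 = 11.2% and 8/100 = 8.0%.
- All 227 treated would give 8/227 = 3.5% and 22/227 = 9.7%.

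At 48 weeks the pattern suggests that discontinuers were kept as not attack-free, while the 227 − 160 = 67 subjects still on drug and short of Week 48 were left out. The SAP states no such rule.

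**2. Apply the written rule to a commercial stop.** Let p be the attack-free proportion among subjects able to complete the window. Let c be the share for whom the commercial stop falls before the window closes, unrelated to attack outcome. None of that share can complete dosing, so none can be attack-free, yet all stay in the denominator:

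reported proportion = p × (1 − c)

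| c | 48 weeks (p = 5.0%) | 24 weeks (p = 9.8%) |
|---|---|---|
| 5% | 4.75% | 9.3% |
| 10% | 4.5% | 8.8% |
| 30% | 3.5% | 6.8% |
| 50% | 2.5% | 4.9% |

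**3. How large c could be at 48 weeks.** The 160 subjects who had already completed or left that window cannot be affected. With 475 enrolled, 475 − 160 = 315 remain exposed, so c cannot exceed 315/475 = 66%. An overall c of 30% to 50% means 143 to 238 subjects, or 45% to 75% of those 315. If 25%, 50% or 100% of the 250 US subjects were stopped before Week 48, the 5.0% would read 5.0% × (475 − 62.5)/475 = 4.3%, 5.0% × (475 − 125)/475 = 3.7%, or 5.0% × (475 − 250)/475 = 2.4%.

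**4. Why dropping administrative stops by reason is not enough.** Among subjects enrolled too late to complete the window, that approach removes those still on drug but keeps those who had already left for lack of efficacy or adverse events. Only failures remain from that group. As an illustration, take c = 30% and suppose that 25.1% of the late group leave early for other reasons (the interim share, 57/227, used as an assumption). The result is 0.050 × 0.70/(0.70 + 0.30 × 0.251) = 0.0350/0.7753 = 4.5%, still below 5.0%. Setting the denominator by opportunity to complete the window returns 5.0%.

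**The case against.** The SAP was written for protocol versions without a commercial stop, so the gap is a version mismatch rather than a faulty rule. This is a fair account of the cause, but these are the analysis rules supplied with the current protocol, and followed as written they misclassify these subjects.

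The Kaplan-Meier analysis already handles such stops, and attack rates use time on treatment. That is true and limits the damage. It does not correct the 24- and 48-week proportions, which will still be tabulated.

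The denominator is inferred from a general convention, and the interim suggests that the sponsor did not apply it literally. This stands as a caution. But the final analysis runs only after the last subject has completed or discontinued, so no group still on drug will remain to be left out. No text extends the interim practice to administrative stops.

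Counting discontinuers as non-responders is a recognised conservative choice. It is reasonable for lack of efficacy, adverse events and voluntary withdrawal. It is hard to defend when the product's arrival on the market ends treatment.

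A reader might also draw three stronger conclusions that the documents do not support:

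- That the gap between 5.0% and 8/227 = 3.5% measures the bias. It does not: 8/227 counts as failures the subjects still on drug at an interim data cut, and the interim summary reports no commercial stops. At 24 weeks the same comparison is 9.8% against 9.7%.
- That 30% to 50% of subjects will be stopped this way. No approval, launch or US enrolment dates are given, and completed filings do not establish the share.
- That the whole-study proportion is also wrong as written. The protocol defines treatment as ending at whichever limit comes first, so a subject who reaches commercial availability has arguably completed dosing. SAP 6.7.8.3 likewise separates completing a period from discontinuing prematurely. The whole-study rule is ambiguous rather than wrong.

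**Conclusion.** The concern holds for the fixed 24- and 48-week windows. Read with the current protocol, the SAP text counts attack-free subjects stopped by commercial availability as failures and so lowers the proportion by the factor (1 − c). At 48 weeks that is a quarter of a percentage point at c = 5%, half a point at 10% and half of the 5.0% at c = 50%. The size rests on an assumed c and on stopping being unrelated to attack outcome. Only subjects without an attack up to the stop are misclassified; those who already had one are correctly not attack-free.

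Severity is minor to moderate. Attack-free status is not a listed endpoint in Protocol 7.1.2 or SAP 3.2.2, no formal testing is planned, a censored analysis already exists, and the bias understates the drug's effect.

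**What to change.** Amend SAP 6.7.8.6 as follows.

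1. For the 24- and 48-week windows, limit the denominator to subjects whose first dose was at least 24 or 48 weeks before the administrative end of treatment at their site or country (commercial availability, transfer to other supply, sponsor decision, or data cut). Apply this whatever the subject's outcome or reason for stopping, and state the denominator in the table.
2. Within that set, keep stops for lack of efficacy, adverse events and voluntary withdrawal as not attack-free.
3. Define when the whole-study period ends for administratively stopped subjects.
4. Report the planned Kaplan-Meier attack-free estimate at Weeks 24, 48 and 96 alongside. It supports the proportions but does not replace them, because it also censors subjects who leave for lack of efficacy.

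The cost is SAP wording, a recorded administrative end date per site or country, and a somewhat smaller denominator. Because eligibility depends on dates, the rule does not need a discontinuation-reason code for commercial availability, which the list in Protocol 8.3.2 does not contain.
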